#### **4.1. Sample Size**

A total of 21 subjects is planned to be enrolled in order to achieve enrolment of 14 subjects in the HIL-214 arm and 7 subjects in the Placebo arm.

The objective of this trial is to evaluate the safety and immunogenicity of two IM injections of HIL-214 in infants aged 5 months ( $\pm 14$  days) at first trial vaccine administration. This trial is designed to be descriptive, and therefore the sample size was not determined based on formal statistical power calculations.

#### **4.2. Randomization, Stratification, and Blinding**

Trial vaccine assignment will be generated by an independent statistician using block randomization stratified by site. The randomization code list will be stored in a secured area, accessible only to authorized unblinded trial personnel. Eligible subjects will be randomized using interactive response technology (IRT) into one of the two trial arms, HIL-214 and Placebo, in a 2:1 ratio, respectively.

When the investigator or designee determines that a subject is eligible to receive trial vaccine, the authorized unblinded trial personnel will randomize the subject to either the HIL-214 or placebo arm of the trial by selecting a randomization code from the ordered randomization code list, using a unique subject number assigned to the subject.

Subjects who are randomized but not dosed will be replaced.

Trial vaccine administration must be done by designated unblinded site staff, in which the trial vaccine is selected using the subject's number. The designated unblinded site staff must not be involved with data collection of any sort including safety evaluation of the subject after administration of the trial vaccine.

The trial blind shall not be broken by the investigator unless information concerning HIL-214 is necessary for the medical treatment of a subject. In the event of a medical emergency, if

possible, the medical monitor should be contacted before the trial blind is broken to discuss the need for unblinding. For unblinding a subject, the trial vaccine assignment will be obtained by an independent authorized unblinded individual who will have access to the randomization code list. The date, time, and reason the trial blind is broken must be recorded in the source document and the same information (except the time) must be recorded on the electronic case report form (eCRF).

If any subject is unblinded, the subject must be withdrawn from the trial and their data no longer evaluated. Subjects should continue to be monitored for safety follow-up.

### **4.3. Analysis Sets**

#### **4.3.1. All Enrolled Set**

The All Enrolled set will include all subjects who were enrolled in the study regardless of whether they were randomized or received study vaccine. This set is used for tables and listings such as subject disposition and screen failures.

#### **4.3.2. Full-Analysis Set (FAS)**

The Full Analysis Set (FAS) will include all subjects who are randomized and received at least one dose of HIL-214 or placebo. The analyses using the FAS will be performed according to the trial vaccine that the subject was randomized to receive.

#### **4.3.3. Per-Protocol Set (PPS)**

The Per-Protocol Set (PPS) will include all subjects in the FAS who have no major protocol deviations. See section 5.2 for definition of major protocol deviations and how these are collected. The PPS will be used as the primary population for analyses of immunogenicity data.

#### **4.3.4. Safety Set (SAF)**

The SAF will consist of all subjects who received at least one dose of HIL-214 or placebo. The SAF will be used as the primary population for analyses of safety data. The analyses using the SAF will be performed according to the trial vaccine actually administered at Visit 1.

## **5. Subject Disposition**

### **5.1. Disposition**

Subject disposition will be summarized for the All Enrolled set. A disposition of subjects includes the number and percentage of subjects for the following categories: subjects who were randomized, subjects who completed vaccine regimen, subjects who withdrew from second dose, subjects who completed the study, subjects who discontinued from the study.

The reasons for withdrawal from second dose will also be summarized in this table. The reason for withdrawal from second dose may include any of the following: Adverse Event, Lost to Follow-up, Withdrawal of Consent, Study Terminated, Death, Protocol Deviation, Other.

The reasons for discontinuation of study participation will also be summarized in this table. The reason for discontinuation of study participation may include any of the following: Adverse Event, Lost to Follow-up, Unblinding, Withdrawal of Consent, PI Decision, Study Terminated, Death, Protocol Deviation, Other.

A summary of the analysis sets includes the number and percentage of subjects for the following categories: subjects in the FAS, PPS and SAF. All percentages will be based on the number of subjects in the All Enrolled set. Two separate tables will be produced, one performed according to the trial vaccine that the subject was randomized to receive and the other according to the trial vaccine that the subject actually received at Visit 1.

Subject disposition data and analysis sets will be presented in listings on the All Enrolled set.

## **5.2. Protocol Deviations**

This section summarises protocol deviations that may greatly impact the completeness, accuracy, and/or reliability of the study data or that may significantly affect subject's rights or safety.

A major protocol deviation is defined as any change or departure from the trial design or procedures of a trial protocol, which affects evaluation of immunogenicity objectives. The following subjects will be considered to have major protocol deviations and therefore excluded from the PPS: (1) not meeting selected entry criteria, (2) receiving wrong or incomplete trial vaccine, (3) receiving prohibited therapies, and (4) other major protocol deviations. Prior to unblinding, all protocol deviations will be reviewed to determine the final list of deviations leading to the exclusions from the PPS.

The following categories of protocol deviations will be reviewed on an ongoing basis with the sponsor prior to database lock to determine those which are considered major deviations as outlined above.

- Subjects not meeting selected entry criteria
- Subjects who received the incorrect dose
- Other deviations that may affect subjects' immunogenicity or safety outcomes.

Such subjects will be identified as part of the data review meeting (DRM) process, prior to database lock.

The number and percentage of subjects with major protocol deviations will be summarised by category. All protocol deviations will be listed. Summaries and listings will be based on the FAS.

## **6. Demographics and Baseline Characteristics**

### **6.1. Demographics**

A summary of demographics and baseline information will be presented. The demographic characteristics consist of age (days), sex, race, and ethnicity. The baseline characteristics consist of baseline length (cm), baseline weight (kg), and baseline head circumference (cm).

Age (days), baseline length (cm), baseline weight (kg), and baseline head circumference (cm) will be summarized using descriptive statistics. The number and percentage of subjects by sex (Male, Female), race (White, Black or African American, Asian, American Indian or Alaska Native, Native Hawaiian or Other Pacific Islander, Multiple and Other) and ethnicity (Hispanic or Latino, Not Hispanic or Latino, Not Reported, Unknown), will also be reported. Percentages will be based on the total number of subjects in the SAF set. Summaries will also be provided for the PPS. If the PPS is less than 0.9 times FAS, demographics and other baseline characteristics will also be summarized based on the FAS.

Subject demographic and baseline characteristics will be presented in a listing for the SAF set.

## **6.2. Medical History**

Medical history will be collected at screening. Medical history will be coded using the latest Medical Dictionary for Regulatory Activities (MedDRA) version. The number and percentage of subjects with any medical history will be summarized overall and for each system organ class and preferred term. Percentages will be calculated based on number of subjects in the SAF set.

Subject medical history data including specific details will be presented in a listing.

## **6.3. Inclusion and Exclusion Criteria**

A listing, based on all enrolled subjects, will be included displaying whether the subject met and/or did not meet the inclusion and exclusion criteria.

A table summarizing screen failures and inclusion/exclusion criteria that subjects did or did not meet will be presented for all enrolled subjects.

# **7. Treatments and Medications**

## **7.1. Prior and Concomitant Medications and Vaccinations**

The following medications, vaccines and blood products received by the subjects are collected on the CRF in the following timeframes:

- All medications used within 2 months prior to the day of first trial vaccine administration through to the time specified up to the end of the trial.
- All vaccines within 14 days before or after either dose of the trial vaccine administration thorough to the time specified up to the end of the trial.
- All blood products used 90 days prior to the day of first trial vaccine administration thorough to the time specified up to the end of the trial.
- All antipyretics and/or analgesic medications within 24 hours prior to trial vaccine administration.

The name of the medication, treatment start and stop dates (or 'ongoing'), dose, route of administration, frequency and indication must be recorded. All medications/vaccinations will be coded according to the latest World Health Organization drug dictionary (WHODrug) version.

A prior medication/vaccination is defined as any medication/vaccination that is taken prior to the first dose of study vaccine (prior to Day 1). The medications could have stopped prior to or be ongoing at the time of study vaccination. A concomitant medication is defined as any medication that has a stop date that is on or after the date of first dose of study vaccination. A concomitant vaccination is defined as any vaccination administered on or after the date of first dose of study vaccination.

For missing and partial dates, medications and vaccinations will be classified in the following way:

**Medications:**

If the start date/end date is prior to the first date of vaccination classed as prior.

If the start date/end date is after the first date of vaccination, classed as concomitant.

Start and/or end date is on the same date as first vaccination will be classed as concomitant.

Medications for which the end date is missing will be classified as concomitant.

Otherwise if there is a partial date that is clearly before or after the first vaccination date, set to be prior or concomitant as appropriate.

**Vaccinations:**

If the administration date is prior to the first date of vaccination classed as prior.

If the administration date is after the first date of vaccination, classed as concomitant.

Administration date is the same date as first vaccination date will be classed as concomitant.

Otherwise if there is a partial date that is clearly before or after the first vaccination date, set to be prior or concomitant as appropriate.

The total number of concomitant medications and the number and percentages of subjects with at least one concomitant medication will be summarized by trial arm. The number and percentages of all concomitant medications will be summarized by trial arm and listed by medication class (Anatomical Therapeutic Chemical (ATC) level 4, if this is not available, the closest ATC level is presented) and preferred term. Prior medications and prior and concomitant vaccinations will be presented similarly to concomitant medications. All summaries will be performed using the SAF.

Prior and concomitant medications and prior and concomitant vaccinations data will be presented in listings. Medication will be flagged as prior (P), concomitant (C) or prior and concomitant (P/C).

## 7.2. Study Vaccine

Subjects will receive the first vaccine at Visit 1 (Study Day 1) and the second vaccine at Visit 2 (between Study Day 29 to 57). The date and time of administration, kit number, injection site and whether the subject was observed for 30 minutes post injection will all be collected on the CRF. Additionally, whether the dose was delayed and reason for delay will be recorded in the subject's CRF.

The number of subjects who received both doses, a summary of the time between both doses in days and the day of dose 2 administration will be summarized on the SAF.

All study vaccine administration data will be presented in a data listing.

## 8. Immunogenicity Analysis

All subjects will have four blood draws: pre-dose 1 (Visit 1 - Baseline), pre-dose 2 (Visit 2), 28 days post-dose 2 (Visit 3), and 6 months post-dose 2 (Visit 4), to measure all anti-norovirus total immunoglobulin (Pan-Ig) and histoblood group antigen (HBGA) blocking antibodies. Unless otherwise stated the immunogenicity analyses will be performed using the PPS. All immunogenicity data will be listed for the FAS. See section 3.2 for a list of the immunogenicity endpoints and summary measures.

### 8.1. Immunogenicity Endpoints

The following evaluations will be performed on the Pan-Ig and HBGA assays:

- Geometric mean titer (GMT) with 95% CI, geometric SD, minimum, maximum, Q1 and Q3. at baseline (Visit 1), Visit 2 (pre-dose 2), Visit 3 (28 days post-dose 2) and Visit 4 (6 months post-dose 2). The 95% CI will be calculated based on the t distribution of the log-transformed values for GMTs, then back transformed to the original scale for presentation.
- Geometric mean fold rise (GMFR) with 95% CI at Visit 2 (pre-dose 2), Visit 3 (28 days post-dose 2) and Visit 4 (6 months post-dose 2) relative to baseline. The 95% CI will be calculated based on the t distribution of the log-transformed values for GMFRs, then back transformed to the original scale for presentation.
- Seroresponse rate (SRR) with 95% CI based on the exact Clopper-Pearson method. Seroresponse is defined as a  $\geq 4$ -fold increase at Visit 2 (pre-dose 2), Visit 3 (28 days post-dose 2) and Visit 4 (6 months post-dose 2) relative to baseline, all considered separately. SRR of GI.1, GII.4 and GI.1 and GII.4 will be analyzed.

The GMT will be calculated using the following formula:

$$10^{\left\{ \frac{\sum_{i=1}^n \log_{10}(t_i)}{n} \right\}}$$

where  $t_1, t_2, \dots, t_n$  are observed immunogenicity titers for  $n$  subjects.

The GMFR measures the changes in immunogenicity titers within subjects. The GMFR will be calculated using the following formula:

$$10^{\left\{ \frac{\sum_{i=1}^n \log_{10} \frac{v_{ij}}{v_{ik}}}{n} \right\}} = 10^{\left\{ \frac{\sum_{i=1}^n (\log_{10} v_{ij} - \log_{10} v_{ik})}{n} \right\}}$$

where, for  $n$  subjects,  $v_{ij}$  and  $v_{ik}$  are observed immunogenicity titers for subject  $i$  at time points  $j$  and  $k = 0$  (Baseline).

Boxplots of titer and fold rise for the pan-Ig and HBGA assays will be plotted. Reverse cumulative distribution curves for the pan-Ig and HBGA assays will also be plotted.

All endpoints will be summarized by both the PPS and FAS.

## 9. Safety Analysis

The purpose of this section is to define the safety parameters for the study and to summarise the safety results. All safety analyses will be conducted on the SAF. Safety measurements will include adverse events (AEs), serious AEs (SAEs), medically attended AEs (MAAEs), solicited AEs, physical examinations and vital signs measurements. Individual subject listings will be provided to support the tables. See section 3.2 for a list of the safety endpoints and summary measures.

Summaries of the day of first onset of each event and the number of days subjects experienced each event will also be provided by event and trial arm on the SAF.

All solicited local and systemic AEs will be presented in a listing.

## **9.2. Unsolicited Adverse Events**

An AE is defined as any untoward medical occurrence in a clinical investigation subject administered a trial vaccine; it does not necessarily have to have a causal relationship with trial vaccine administration. An AE can therefore be any unfavorable and unintended sign (e.g., a clinically significant abnormal laboratory finding), symptom, or disease temporally associated with the administration of a trial vaccine whether or not it is considered related to the trial vaccine.

Unsolicited AEs are collected through 28 days post-first and second vaccination. AEs leading to trial vaccine withdrawal are collected up to the second trial vaccine dose administration. SAEs, AEs leading to withdrawal from trial and MAAEs are collected for the entire study period.

The reported term for the unsolicited AE, start and end date, seriousness, severity, relationship to trial vaccine or trial procedure, action taken and outcome of event will be collected on the eCRF.

Summaries of the total number of unsolicited AEs and the number and percentage of subjects with at least one AE will be provided by trial arm. AEs will be presented by SOC and PT. At each level of subject summarization, a subject is counted once if the subject reported one or more events. Percentages will be calculated out of the number of subjects in the SAF. The summary of AEs will be presented in descending order from the SOC with the highest total incidence to the SOC with the lowest total incidence. If the total incidence for any two or more SOCs is equal, the SOCs will be presented in alphabetical order. Within each SOC, the PTs will be presented in alphabetical order.

Summaries of unsolicited AEs will be presented as follows after both vaccines (individually and combined):

1. Overall up to 28 days after trial vaccine administration;
2. With onset between Day 1 and Day 7 after each dose (including the day of trial vaccine administration);
3. With onset between Day 8 and Day 29 after each dose (including the day of trial vaccine administration).

Any AE reported between Day 29 and the second vaccination (up to Day 57) will be included in the listed.

Unsolicited AEs will be coded by PT and SOC using the latest MedDRA version.

For missing/partial start and end dates, the rules stated in Section 4 will be followed.

All AEs will be presented in a listing.

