7.5 Criteria for Premature Discontinuation of Trial Vaccine Administration

There are circumstances under which receipt of a further trial vaccine dose is a contraindication in this trial. These circumstances include anaphylaxis or severe hypersensitivity reactions after the first trial vaccine administration. If these reactions occur, the subject must not receive additional trial vaccine but the subject's LAR is encouraged to allow the child to continue participating in the trial for safety follow-up.

Early termination of a subject's trial participation will by default prevent the subject from receiving further doses of trial vaccine, as the subject will no longer be participating in the trial. In addition to criteria for early termination of a subject's participation (see Section 7.4), other situations may apply in which subjects may continue participating in the trial (e.g., contributing safety data according to the protocol) but trial vaccine administration is discontinued. Even if the subject is deemed ineligible to receive further doses of trial vaccine, all efforts should be made to continue the collection of safety data according to the protocol.

In addition, the primary reason for premature discontinuation of trial vaccine administration should be recorded in the electronic case report form (eCRF, end of trial vaccine administration page) using the following categories:

1. **Adverse Event:** The subject has experienced an AE (irrespective of being related/unrelated to the trial vaccine or trial-related procedures) for which subsequent trial vaccine administration(s) pose an unacceptable risk to the subject's health, but the subject will continue trial participation for safety, or a subset of other trial procedures.
2. **Lost to follow-up:** The subject did not return to the clinic and at least three documented attempts to contact the subject's LAR were unsuccessful.
3. **Withdrawal of consent:** The subject's LAR wishes the subject to withdraw from the trial. The primary reason for early termination will be withdrawal of consent if the subject withdraws from participation due to a non-medical reason (i.e., reason other than an AE). The reason for withdrawal, if provided, should be recorded in the eCRF.
4. **Premature trial termination by sponsor, a regulatory agency, the IRB, or any other authority.**

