9.3 Schedule of Observations and Procedures

The schedule of procedures is shown in Section 2.3. Assessments should be completed at the designated visit(s)/time point(s). In the event that the second dose of trial vaccine is not administered, no blood will be collected at Visit 3 and Visit 4, however these visits should be conducted for safety monitoring at time points relative to the window during which the second dose was to be administered.

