#### **9.2.1. Relationship of Unsolicited Adverse Events to Vaccine and Study Procedure**

Relationship to the trial vaccine will also be assessed by the investigator. The relationship of each unsolicited AE to the trial vaccine will be assessed using the following categories:

**Related:** There is suspicion that there is a relationship between the trial vaccine and the AE (without determining the extent of probability); there is a reasonable possibility that the trial vaccine contributed to the AE.

**Not Related:** There is no suspicion that there is a relationship between the trial vaccine and the AE; there are other more likely causes and administration of the trial vaccine is not suspected to have contributed to the AE.

A summary of unsolicited AEs by relationship (i.e. “Related” and “Not Related”) to trial vaccine will be presented in a table by incidence of occurrence. If a subject reports multiple occurrences of the same AE, only the most related occurrence will be presented. AEs that are missing a relationship will be presented in the summary table as “Related” but will be presented in the data listing with a missing relationship. Percentages will be calculated out of the number of subjects in the SAF.

The unsolicited AE data will be categorized and presented by SOC, PT, and relationship up to 28 days after both vaccinations separately.

Relationship to trial procedures should also be determined for all unsolicited AEs. Relationship to trial procedures will be summarized in the same way as relationship to trial vaccine.

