#### **9.2.2. Severity of Unsolicited Adverse Event**

A summary of unsolicited AEs by severity will be presented in a table. The severity that will be presented represents the most extreme severity captured on the CRF page. The possible severities are “Mild”, “Moderate”, and “Severe”. In the unsolicited AE severity table, if a subject reported multiple occurrences of the same AE, only the most severe will be presented. Unsolicited AEs that are missing severity will be presented in tables as “Severe” but will be presented in the data listing with a missing severity. Percentages will be calculated out of the number of subjects in the SAF.

The unsolicited AE data will be categorized and presented by SOC, PT, and severity up to 28 days after both vaccinations separately.

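### Post-dose-2 unsolicited AE percentages divide by everyone who had at least one dose, so each missed second dose dilutes the printed rate

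*SAP*

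**What the plan says.** The layout sentence in SAP 9.2 begins "Summaries of unsolicited AEs will be presented as follows after both vaccines (individually and combined" and goes on to list three onset windows. The denominator sentence in the same section is "Percentages will be calculated out of the number of subjects in the SAF". The two subsections that follow use the same denominator and are also split by dose:

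- SAP 9.2.1: "The unsolicited AE data will be categorized and presented by SOC, PT, and relationship up to 28 days after both vaccinations separately".
- SAP 9.2.2: "The unsolicited AE data will be categorized and presented by SOC, PT, and severity up to 28 days after both vaccinations separately".

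SAP 4.3.4 defines the set: "The SAF will consist of all subjects who received at least one dose of HIL-214 or placebo". Protocol 13.1.1 agrees. The default in SAP 4 is the arm size within the analysis set unless something else is specified, and 9.2 specifies nothing else for post-dose-2 tables.

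The documents expect that some infants may stop after dose 1. SAP 5.1 tabulates withdrawal from the second dose, with reasons. Protocol 7.5 wants safety data to continue "Even if the subject is deemed ineligible to receive further doses of trial vaccine". Protocol 9.3 provides for the case that opens "In the event that the second dose of trial vaccine is not administered": no blood is drawn at Visits 3 and 4, but both visits go ahead for safety. Such infants are not replaced, because the only replacement rule is "Subjects who are randomized but not dosed will be replaced" (SAP 4.2).

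SAP 9.1 treats solicited events differently. Its by-day tables use SAF participants who reported data for the category and day. Its Day 1–7, 1–3 and 4–7 summaries, repeated by dose, state no denominator.

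**The concern.** A post-dose-2 percentage should describe infants who were at risk in that window. An infant without dose 2 has no such window, because the SAP counts it from vaccine administration. The safety visits kept under Protocol 9.3 do not create one. As written, that infant is treated in the percentage as if dosed and free of events.

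Unsolicited AEs up to 28 days after each dose are a primary endpoint, and the primary objective is safety compared with placebo. Infants stopped because of an AE after dose 1 would be among those carried as having no event after dose 2. The dilution therefore flatters the arm with more such stops. Because the arms are 14 and 7, the same number of missed doses also weighs twice as heavily on placebo.

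**Working it through.** **Inputs.** N = 14 (HIL-214) and 7 (placebo), from SAP 4.1; these match 2:1 allocation of 21, since 21 × 2/3 = 14 and 21 × 1/3 = 7. The plan states no post-dose-2 rate, dropout rate or power figure, so there is no figure of its own to reproduce. Let m be the infants in an arm who miss dose 2 and x those with an event after dose 2. Both are assumptions here.

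**Formula.** Printed rate = x/N. Rate among dose-2 recipients = x/(N−m). So printed = recipient rate × (N−m)/N, a relative fall of m/N.

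| m | HIL-214 factor | Relative fall | Placebo factor | Relative fall |
|---|---|---|---|---|
| 0 | 1.000 | 0 | 1.000 | 0 |
| 1 | 13/14 = 0.929 | 7.1% | 6/7 = 0.857 | 14.3% |
| 2 | 12/14 = 0.857 | 14.3% | 5/7 = 0.714 | 28.6% |
| 3 | 11/14 = 0.786 | 21.4% | 4/7 = 0.571 | 42.9% |

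**Largest absolute shift, m = 1.** HIL-214: 13/13 prints as 13/14, 7.1 points low. Placebo: 6/6 prints as 6/7, 14.3 points low.

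**Effect on the comparison.**

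- One placebo infant misses dose 2 and no HIL-214 infant does: 7/14 and 3/6 are both 50.0%, but print as 50.0% and 3/7 = 42.9%. That is a 7.1-point difference with no basis in the data.
- Two HIL-214 infants miss dose 2: 6/12 = 50.0% prints as 6/14 = 42.9%, lower by 7.1 points.
- One missed in each arm: a common recipient rate p prints as 0.929p and 0.857p, a gap of p × (13/14 − 6/7) = p/14. At an assumed p of 50% the rates are 46.4% and 42.9%, a gap of 3.6 points.
- Two missed on HIL-214 and one on placebo: both factors are 0.857. The ratio of rates is preserved, but both rates are low.

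**Against sampling error.** Exact 95% limits are 11.8–88.2% for 3/6 and 9.9–81.6% for 3/7, which overlap almost entirely.

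**Could m be above zero?** If each infant had an assumed chance q of missing dose 2, at least one of 21 would miss it with probability 1 − (1−q)^21: 35%, 66% and 89% for q = 2%, 5% and 10%.

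**Can a reader undo it?** Yes, with the arm-level m, by multiplying by N/(N−m): 14/13 = 1.077 or 7/6 = 1.167 for m = 1. For example, 3/7 × 7/6 = 3/6.

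**The case against.** The best defence has four parts.

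1. The protocol and SAP set these measures in the SAF, and x over the SAF is a defined quantity: the share of vaccinated infants who had an event after a second dose. That is true, but a table headed by dose will be read as the rate after that dose. For an infant without the dose it is not one.
2. The table shells are not in the documents. They may carry by-dose Ns, and SAP 4 allows a row for missing values to account for dropouts where the shells ask for it. Such a row could show these infants as missing, but it would not change the denominator. If the shells do use by-dose Ns, the SAP text contradicts them and still needs correcting.
3. The effect may never arise, does not alter counts, and feeds no test or decision rule. SAP 5.1 and 7.2 tabulate second-dose withdrawals and receipt of both doses, so the rate can be recovered. All of this stands and limits the weight of the point, though a reader should not have to recompute a primary safety percentage.
4. Dose-2 recipients are a selected group, having gone on after dose 1. This also stands, and belongs beside the table as a caveat.

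A reader might infer that the fault runs through all solicited summaries. It does not. The reported-data rule in SAP 9.1 already removes infants without dose 2 from the by-day tables. The temperature, first-onset and duration summaries are not described as split by dose.

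A reader might also infer that the arm for an infant given one dose of each product is undecided in post-dose-2 tables. SAP 4 moves such an infant to HIL-214 only for any-dose or overall results. Elsewhere the Visit 1 product governs (SAP 4.3.4, Protocol 13.1.1), and SAP 5.1 uses the actual vaccine in that same sense. At most this is a remote matter of wording.

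**Conclusion.** The point holds for the post-dose-2 unsolicited AE tables in SAP 9.2, 9.2.1 and 9.2.2. By a narrower route it extends to the by-dose Day 1–7, 1–3 and 4–7 solicited summaries in SAP 9.1, which name no denominator and so may fall back on the SAP 4 default. The SAF remains the right denominator for post-dose-1, combined and whole-trial tables.

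The understatement is m/N relative. It depends entirely on m, which the documents do not give, and on the SAP text being followed literally. It should be corrected because it concerns a primary endpoint and can distort the arm comparison even when equal numbers miss dose 2. It does not threaten the trial's conclusions: the study is descriptive and its arms are too small for a shift of this size to stand out. Nothing in the documents shows that any infant will miss dose 2, so a claim that the reported rates will be biased would go too far.

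**What to change.** In SAP 9.2, 9.2.1 and 9.2.2, add wording to this effect: *Post-dose-2 tables use as denominator the SAF subjects in the arm who received dose 2, and that N is shown in the table. Post-dose-1, combined and whole-trial tables use the full SAF.*

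In SAP 9.1, apply the same by-dose denominator to the Day 1–7, 1–3 and 4–7 post-dose-2 summaries. Check the shells against the revised text.

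The cost is a few sentences and some table programming, with no new data. There are two downsides. Post-dose-2 rates will describe infants who went on to dose 2, so a footnote should give the number who did not, with the reasons already collected for SAP 5.1. Column Ns may also differ between tables.
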